## **5.2. Sample Size Estimate**

When the sample size is 108 images of both the OCT and IVUS catheters, a two group 0.05 one-sided matched t-test will have 90% power to reject the null hypothesis that the test (OCT) and standard (IVUS) are not equivalent in favor of the alternative hypothesis that the two groups are equivalent. To obtain 108 vessel segment images at five images per subject, 22 subjects would be needed; however, recognizing that some images (~ 5%) may be of poor quality and illegible, 25 subjects should be enrolled and 115 images evaluated.

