## **5.3. Study Endpoints**

Primary efficacy endpoint is met when OCT imaging has the equivalent or higher ranking of IVUS imaging of the visualization of vessel morphology and disease for:

- Layered structure – intima, media, external elastic lamina, and adventitia;
- Non-layered structure—presence of disease in the vessel structure;
- Abnormal physiology—dissection/tissue flap/false lumen, thrombus, calcium;
- Bifurcation of the vessel; and
- Frequency of artifacts.

Secondary efficacy endpoint is met when OCT imaging has the equivalent dimensions of vessel diameter and total luminal area as that determined with IVUS imaging.

Primary safety endpoint is freedom from diagnostic imaging procedure-related and device-associated adverse events, as reported by the physician.

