### **6. STUDY PROCEDURE**

#### **6.1 Gathering OCT and IVUS Images**

After providing informed consent, the subject will be prepared for the diagnostic procedure according to the institution’s and investigator’s standard procedures. Demographic information will be recorded for each subject.

A radiopaque ruler will be attached to the subject’s leg to provide reference marks for starting and stopping points of the “target segment” that will be used for image acquisition by the two devices.

Subjects will undergo diagnostic angiographic images to identify the target segment starting point (distal end) and ending point (proximal end) which will be between 5 cm and 10 cm within the vessel.

A 7 Fr vascular sheath will be advanced up-and-over the aortic bifurcation and to the region of interest of the artery.

A 0.014 inch guide wire will be advanced distal to the target segment under angiographic imaging.

An IVUS catheter will be loaded onto the wire and advanced until its imaging transducer resides at the distal end of the target segment (starting point). Using the radiopaque ruler as a reference of the starting point (distal end) and stopping point (proximal end) of the target segment, the IVUS catheter will be energized for imaging and retracted through the target segment (between 5 cm and 10 cm within the vessel) capturing images within the target segment.

The diameter of the lumen of the vessel at the starting, mid, and ending points of the target segment will be measured using the IVUS system software. Mean diameter and luminal area will be calculated for each target segment imaged.

After all images and measurements of the target segment have been captured on the IVUS system, the IVUS catheter will be removed.

Using the radiopaque ruler as a reference, an OCT catheter will be advanced over the 0.014 guide wire until its imaging window is at the exact same starting point (distal end) of the target segment. Once the OCT catheter is inserted, the subject is enrolled in the study. With the device energized, the OCT catheter will be retracted through the exact same target segment of the vessel and the OCT images captured on the Lightbox system.

The diameter of the lumen of the vessel at the starting, mid, and ending points of the target segment will be measured using the OCT system software. Mean diameter and luminal area will be calculated for each target segment imaged.

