### 6.3 Statistical Analyses

Statistical analyses will be carried out using StatView software (SAS Institute, Cary, NC). A  $p$  value  $< 0.05$  will be considered statistically significant. Matched Pairs  $t$ -Test will be performed to compare means and on paired samples to compare procedural data and complications associated with the imaging techniques. The mean values of the results of all readings of all readers will be calculated for comparison of image quality. Fisher's Exact Test will be used to compare proportions. The Mann-Whitney-Wilcoxon test will be applied for statistical comparison of the results for OCT and IVUS imaging. Interreader and intrareader reproducibility will be calculated by intraclass correlation (ICC) analysis in a two-way mixed model. Correlation of the mean values of the results of the quantitative measurements of all readers with both imaging modalities will be calculated as Pearson correlation coefficient.

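### The secondary endpoint requires equivalent dimensions, but the plan sets no margin or decision rule and assigns no test; Pearson's r, the only analysis tied to quantitative measurements, cannot show equivalence

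*Combined protocol and SAP*

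**What the plan says.** - **Endpoint (5.3 Study Endpoints).** "Secondary efficacy endpoint is met when OCT imaging has the equivalent dimensions of vessel diameter and total luminal area as that determined with IVUS imaging". This is a met/not-met statement with no margin, limits of agreement or success rule.
- **Data (6.1 Gathering OCT and IVUS Images).** Lumen diameter is measured with each system's software at the start, middle and end of the target segment. Then "Mean diameter and luminal area will be calculated for each target segment imaged". This says how the values arise, not how they are judged.
- **Analysis (6.3 Statistical Analyses).** The secondary endpoint is not mentioned. Results of the "quantitative measurements of all readers with both imaging modalities will be calculated as Pearson correlation coefficient", with no threshold. The matched-pairs t-test "will be performed to compare means and on paired samples to compare procedural data and complications associated with the imaging techniques", without saying whether diameter and area are among the means. The only general criterion is p < 0.05.
- **Sample size (5.2 Sample Size Estimate).** For 108 images of each modality, "a two group 0.05 one-sided matched t-test will have 90% power to reject the null hypothesis" of non-equivalence "in favor of the alternative hypothesis that the two groups are equivalent". No margin, SD or endpoint is named.

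**The concern.** An equivalence claim needs a stated largest acceptable difference and a rule that compares the data with it. Here both are absent, so whoever analyses the data must choose the rule, possibly after seeing the results.

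The methods that 6.3 offers make poor substitutes. A high r is compatible with a large systematic difference between devices. A non-significant t-test becomes more likely as measurement gets noisier, so poor precision would favour an equivalence claim. Conversely, a trivial difference measured precisely could be taken as failure. What is at stake is the credibility of any statement that OCT lumen measurements can be used interchangeably with IVUS measurements.

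**Working it through.** **1. The plan's own figure.** The 108 in 5.2 cannot be reproduced forwards, because no margin, SD or expected difference is given. Solved backwards for 108 independent pairs, one-sided 0.05, 90% power and no true difference, with the normal approximation:

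- two one-sided tests (TOST): (1.645 + 1.645)/√108 = 0.317 SD of the paired difference (exact t calculation 0.319);
- a single one-sided test: (1.645 + 1.282)/√108 = 0.282 SD (exact 0.283).

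Neither margin is in the documents. They belong to an unnamed image-level outcome and say nothing in millimetres about diameter or area.

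**2. Assumptions for the illustrations (none is in the documents).** 25 pairs, that is one target segment per subject at the planned enrolment; true diameter T with mean 5 mm and SD 1 mm; equal error SD s per device; IVUS = T + e1; OCT = (1 + b)T + e2; circular lumen, so the area bias is (1 + b)² − 1.

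**3. Pearson's r.** Expected r = (1 + b)/√[(1 + s²)((1 + b)² + s²)]. With s = 0.25:

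- b = 0: 1/1.0625 = 0.941;
- b = 0.10: 1.10/√(1.0625 × 1.2725) = 1.10/1.1628 = 0.946, although area is overstated by 1.10² − 1 = 21%.

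A constant shift leaves r exactly unchanged. Here a proportional bias raises it slightly.

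**4. Matched t-test used as a test of difference, two-sided 0.05.** The paired difference has mean 5b and SD √(b² + 2s²). For b = 0.05 and s = 0.25 that is 0.25 mm and √(0.0025 + 0.125) = 0.357 mm, so the noncentrality is 0.25 × √25/0.357 = 3.50. Probability of a non-significant result:

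| OCT too large by | s = 0.1 mm | s = 0.25 mm | s = 0.5 mm |
|---|---|---|---|
| 2% | 8% | 73% | 89% |
| 5% (area +10%) | 0% | 8% | 61% |
| 10% (area +21%) | 0% | 0% | 8% |

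Along each row the bias is fixed and only precision worsens, yet the chance of finding no significant difference never falls and mostly rises. At the other extreme, a 2% bias measured with s = 0.1 mm is significant in about 92% of trials.

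**5. What an equivalence rule could deliver.** Paired TOST at one-sided 0.05, one segment mean per subject, true difference exactly zero (the best case):

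| Margin / SD of paired differences | 25 subjects | 22 subjects |
|---|---|---|
| 0.4 | 25% | 17% |
| 0.5 | 57% | 47% |
| 0.6 | 80% | 72% |
| 0.7 | 92% | 87% |

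80% power needs a margin of 0.603 SD with 25 subjects and 0.645 SD with 22. If a true difference exists, power is lower: at a margin of 0.6 SD with 25 subjects it is 74% for a difference of 0.1 SD and 60% for 0.2 SD.

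**The case against.** **Section 5.2 already sets up an equivalence test.** The matched t-test is named in both sections, and 6.3 states no null hypothesis. One may therefore read the hypotheses of 5.2 into 6.3. That is fair, and it means the documents do not establish that the t-test in 6.3 is a test of difference. A reader might infer that the t-test in 6.3 can never show equivalence; that is too strong, since with a margin the same paired data could support one. But this reading does not close the gap: without a margin and a link to diameter and area, there is nothing to test against.

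**The plan does not say that a high r or a non-significant p value means success.** Correct. A reader might infer that the protocol makes r the success criterion, or that a small but significant difference would count as failure. Neither is written. They are uses that an unspecified plan leaves open.

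**The 108-image calculation applied to dimensions.** A reader might apply the margin implied by 108 images to about 25 segment means and conclude that there is almost no power. The documents do not support that step: the outcome, unit and SD differ, and 5.2 names no endpoint. What follows is only that the 90% power in 5.2 cannot be claimed for this endpoint.

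**The illustrations rest on assumed error.** This also stands. A 10% bias is nearly always detected in the table. The large miss rates come from the highest error assumed or from a 2% bias that may not matter. The figures show the mechanism, not the actual risk.

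**Possible missing text.** Section 6.3 speaks of measurements by all readers, whereas 6.1 uses system software. The available text of 6.2 has a break where a reader measurement task may have stood, so this mismatch is not counted as a defect. It would not explain the absence of a decision rule from 5.3 and 6.3.

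**Conclusion.** The point holds. The plan declares a met/not-met equivalence endpoint for diameter and luminal area and provides no margin, decision rule or assigned analysis for it. That conclusion rests on the text alone. Pearson's r cannot fill the gap, because it hardly responds to systematic bias. The matched t-test would fill it only if a margin and hypotheses for these dimensions were supplied.

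The size is illustrative. Under the stated assumptions, r is 0.941 without bias against 0.946 with a 10% bias, and a 5% bias goes undetected by a difference test in about 0% to 61% of trials, depending on measurement error. The number of segments per subject is also an assumption, because 6.1 does not fix it. As this is a secondary endpoint, the change should be made, but the point does not by itself undermine the trial's primary comparison.

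**What to change.** Add to 6.3 one analysis assigned to the secondary endpoint:

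- **Estimand and rule.** The mean paired OCT minus IVUS difference in segment mean diameter and in luminal area (the 6.1 values), each with a 90% confidence interval. The endpoint is met only if both intervals lie inside their margins, which is paired TOST at 0.05. Because both must pass, alpha need not be split.
- **Margins.** One for diameter and one for area, justified by the sponsor and fixed before the data are seen.
- **Unit.** One segment mean per subject, or a model with a subject effect if single points or several segments are analysed. Treating 75 points (25 subjects × 3) as independent is not a remedy: at a within-subject correlation of 0.5 and a true difference at a margin of 0.5 point-level SD, false equivalence is about 12% instead of 5%.
- **Source.** State whether software or reader measurements are used.
- **Other statistics.** Keep Pearson's r as descriptive only. Bland-Altman limits of agreement are optional support.
- **Power.** State it for this endpoint rather than relying on 5.2.

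The cost is a few sentences, two justified margins and a power statement, with no added measurement if the 6.1 values are used. The downside should be stated openly: with one segment per subject and exactly zero true difference, power per dimension is below 80% if the margin is under about 0.60 SD of the paired differences with 25 subjects (0.65 with 22). It is lower with any true difference, and power for both dimensions together cannot exceed the lower of the two.

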## 7. SAFETY AND DEVICE MALFUNCTION REPORTING

### 7.1. Safety Reporting

Incidence and severity of procedure-related and device-related adverse events (*e.g.*, vessel spasm, thrombosis, distal embolism, *etc.*) will be evaluated following each scan and documented over the course of the study. All adverse events (AEs) will be required to be completely documented through Avinger's complaint handling process..

The following events will be considered to be serious adverse events (SAEs) and must be reported to the Sponsor by telephone, fax and/or email. These events must be reported whether or not the Investigator believes they are related to study procedures, activities or device:

- Death;
- Life-threatening event;
- Disability – significant, persistent, or permanent change, impairment, or damage or disruption in the subject's body function/structure, physical activities or quality of life;
- Necessitate immediate medical or surgical intervention to:
  - Preclude permanent impairment of a body function or permanent damage to a body structure
  - Relieve unanticipated temporary impairment or damage; or
- Prolongation of a hospitalization.

It is the responsibility of the Investigator to inform their Institutional Review Board (IRB) of serious adverse events as required by their IRB's procedures and in conformance with local regulatory requirements.

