#### **5.5. Duration of Subject Participation**

Participation lasts the duration of the diagnostic imaging procedure. No follow-up imaging or patient data will be collected.

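### The SAE list in Section 7.1 covers a prolonged hospital stay but not a new unplanned admission, so some admissions for a complication meet no seriousness criterion

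*Combined protocol and SAP*

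**What the plan says.** Section 7.1 of the protocol introduces its list with "The following events will be considered to be serious adverse events (SAEs) and must be reported to the Sponsor by telephone, fax and/or email". Five items follow: death, a life-threatening event, disability, a need for immediate intervention, and "Prolongation of a hospitalization". The intervention item opens with "Necessitate immediate medical or surgical intervention to" and has two limbs: preventing permanent impairment or damage, and "Relieve unanticipated temporary impairment or damage".

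The section attaches three duties to the listed events. They go directly to the sponsor. Causality is not a filter: "These events must be reported whether or not the Investigator believes they are related to study procedures, activities or device". The investigator must also inform the IRB of serious events, following that board's procedures and local requirements.

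Other adverse events have their own route: "All adverse events (AEs) will be required to be completely documented", through the sponsor's complaint handling process.

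On timing, Section 5.5 says "Participation lasts the duration of the diagnostic imaging procedure" and that no patient data are gathered afterwards. Sections 5.4 and 6.1 have the subject leave the study once OCT imaging and measurements are finished.

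**The concern.** Whether an event is serious should depend on the event and its consequences. Under this list it can depend on whether the subject was already in a hospital bed. An access-site hematoma that leads to one night of observation is serious in an inpatient whose stay is extended, but meets no item in a subject who came from home.

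The label matters because 7.1 hangs the direct report and the IRB notification on it, and Section 11.3 makes failure to report SAEs a possible reason for suspending or terminating a center. Sites are therefore held to this list. Three sites applying it could classify the same admission differently.

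**Working it through.** No arithmetic applies, and there is no figure in the plan to reproduce. The check is a reading of 7.1 against the rest of the protocol.

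**Step 1: is the list a definition or a set of examples?** "The following events will be considered to be serious adverse events (SAEs) and must be reported to the Sponsor" is followed directly by the items, with no wording that marks them as illustrative. Where the same section does give examples, of procedure- and device-related adverse events, it marks them as such. The list reads as the definition.

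**Step 2: is seriousness defined anywhere else?** Sections 11.3 and 11.4 refer to reporting of SAEs and AEs without defining them. Section 9 cites ISO 14155 and ICH E6 in general terms and brings in no definition. No other section adds hospital admission as a criterion.

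**Step 3: apply the list to admissions.** Each case assumes no death, life threat or disability.

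| Case | Item met | SAE under 7.1? |
|---|---|---|
| Inpatient, stay extended to observe a hematoma | Prolongation | Yes |
| Not in hospital, admitted to observe the same hematoma | None | No |
| Not in hospital, admitted, immediate intervention to prevent permanent damage | Intervention, first limb | Yes |
| Not in hospital, admitted, immediate intervention for an unanticipated temporary impairment | Intervention, second limb | Yes |
| Not in hospital, admitted, immediate treatment of a temporary impairment regarded as anticipated | None | No |

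The second and fifth rows are the gap. The fifth is realistic: Section 3.1 names hematoma, puncture-site bleeding, spasm, embolism, dissection and thrombosis among the known risks, and 7.1 does not say what counts as unanticipated.

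**Step 4: what does an event in the gap still trigger?** It is documented through the complaint process. It still counts against the primary safety endpoint in Section 5.3 if it is related to the imaging procedure or a device, because that endpoint has no seriousness threshold. It does not trigger the SAE report to the sponsor made regardless of causality, or the IRB notification in 7.1.

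**Step 5: would the study see the admission?** An overnight stay falls after the exit point in 5.4 and 6.1 and after the participation period in 5.5. No section states a period over which later hospital events are ascertained. The existing prolongation item has the same difficulty.

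**The case against.** The strongest reply is that the gap is narrow and its consequences limited. Most of that reply stands.

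- The intervention item already makes many admissions serious. A reader might infer that any outpatient admitted for a catheter complication escapes SAE reporting. The third and fourth rows of the table show otherwise.
- The sponsor still receives the event, because the complaint process is its own, and Section 11.1 requires adverse events in the source records. A reader might infer that a safety signal would emerge late. The documents do not support this: 7.1 sets no deadline for either route, so no delay can be shown.
- A reader might infer that a reported SAE rate would be biased. Neither Section 5.3 nor Section 6.3 plans an SAE rate as an endpoint or a named analysis.
- IRB duties in 7.1 follow each board's procedures and local rules, so a board may require more than the list does. That is a possible backstop, but it does not repair the protocol's own definition.
- Hospitalization is not defined, so a site might treat an unplanned overnight stay after a hospital-based procedure as prolongation. This makes the wording ambiguous as well as incomplete, and invites inconsistent classification.
- Exposure is reduced because enrollment occurs when the OCT catheter is introduced, and the fourth inclusion criterion in Section 5.1 requires IVUS imaging and removal without adverse events. Complications recognized at the IVUS stage therefore precede enrollment. The OCT stage, and complications recognized later, remain.

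None of these points supplies a criterion for a new admission.

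**Conclusion.** The concern holds as a gap in classification. For a subject not already in hospital, admission because of a complication is not in itself serious under 7.1, while the same event prolonging an inpatient's stay is. The affected cases are admissions for observation only and admissions for a temporary impairment regarded as anticipated. The primary safety endpoint is not affected.

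The size cannot be put as a number. Up to 25 subjects are planned, but the documents do not say how many will be outpatients or how often such admissions are expected. The conclusion assumes that sites read the list as complete, as its wording suggests, and that at least some subjects are not inpatients when imaged. It is worth correcting because the rule as stated sorts like events differently and the correction is short.

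**What to change.** Change the last bullet of 7.1 to read: *unplanned hospital admission or prolongation of an existing hospitalization*. Check that the adverse event report form, which is not among the documents reviewed, uses the same wording.

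State the period after the imaging procedure over which admission or prolongation is ascertained, and reconcile it with the exit wording in 5.4 and 6.1 and the no-follow-up wording in 5.5. Without this, the revised bullet would classify admissions correctly but would not ensure that they are found.

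The cost is a few words in 7.1 and on the form, a brief check after the procedure, and possibly a few more events reported as serious. Neither the imaging procedure nor the efficacy analysis changes.

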### 7.2. Device Malfunction and/or Device Failure Reporting

All reported device malfunctions or failures of the Pantheris Catheter, Imaging Sled, or Lightbox Console are required to be completely documented through Avinger's complaint handling process. All malfunctions or suspected failures of the Pantheris catheter shall be returned to Avinger for analysis with instructions provided by Avinger. Any malfunctions or suspected failures of the IVUS device should be reported to its manufacturer.

NOTE: Device failures or malfunctions are **NOT** to be reported as adverse events. However, if there is an adverse event associated with a device failure or malfunction, the specific event should be recorded on the adverse event report form.

